Describe other resources available to conduct the research.

16.2 Describe the time and effort that the Principal Investigator and research staff will devote to conducting and completing the research.

NOTE: Examples include the percentage of Full Time Equivalents (FTE), hours per week. The question will elicit whether there are appropriate resources to conduct the research.

Response:

The time that will be allotted to research will be equivalent to 8 FTE hours per week. This time will be utilized to:

- Fabricate each in-office appliance and mandibular essix retainer for the subjects included in the study
- Collect, store, and organize all records and data for each subject
- Perform necessary orthodontic adjustments for each patient
- Analyze data collected and work on the statistical analysis
- 16.3 Describe the availability of medical or psychological resources that subjects might need as a result of anticipated consequences of the human research, if applicable.

NOTE: One example includes: on-call availability of a counselor or psychologist for a study that screens subjects for depression.

Response:

The design of the study maintains minimal risk given that the orthodontic treatment is routine. The additional radiation received by patients when taking the additional lateral cephalogram for T1 measurements is minimal. In the United States, annual natural background radiation exposure, which does not include medical exposure or exposure through consumer products, is around 3.1 mSv. Average annual medical radiation exposure is around 3.0 mSv, and average total annual exposure including background, medical, and consumer exposure is around 6.1 mSv.²¹ A standard lateral cephalogram taken at the University at Buffalo School of Dental Medicine's Orthodontic clinic is around 0.6577 mSv, and therefore the exposure would be minimal in comparison.

All subjects will have access to all orthodontic resources they might need. If questions or concerns arise throughout treatment, all subjects will have access to the University at Buffalo School of Dental Medicine's

Page 29 of 49

Orthodontic Clinic emergency hotline, which will be able to route them to an on-call orthodontics resident, who can contact the PI. There are emergency procedures in place as well which they can access if necessary, during any time in the treatment. If the patient experiences any psychological distress throughout the study, there are resources available which can easily be accessed.

16.4 Describe your process to ensure that all persons assisting with the research are adequately informed about the protocol, the research procedures, and their duties and functions.

Response:

The research protocol will be available in both hard copy and electronic copy for all who are involved in the study. A streamlined version of the protocol will also be available for those involved. There will be a presentation for orthodontic residents, faculty and staff before patient recruitment commences in order to ensure that everyone who is involved can ask any questions and understands the workflow of the protocol. During this presentation, the duties and responsibilities of those who are involved will be explained and addressed.

17.0 Other Approvals

1.1 Describe any approvals that will be obtained prior to commencing the research (e.g., school, external site, funding agency, laboratory, radiation safety, or biosafety).

Response:

N/A: This study does not require any other approvals.

18.0 Provisions to Protect the Privacy Interests of Subjects

18.1 Describe how you will protect subjects' privacy interests during the course of this research.

NOTE: Privacy refers to an individual's right to control access to him or herself. Privacy applies to the person. Confidentiality refers to how data collected about individuals for the research will be protected by the researcher from release. Confidentiality applies to the data.

Examples of appropriate responses include: "participant only meets with a study coordinator in a classroom setting where no one can overhear", or "the participant is reminded that they are free to refuse to answer any questions that they do not feel comfortable answering."

Response:

During the recruitment phase, the purpose and protocol of the study will be explained to patients in an enclosed, private setting containing the primary investigator, treating resident, subject, and subject guardian only. The participants

Page 30 of 49

at any point are free to refuse treatment and anything during treatment that they do not feel comfortable with. The patients have the authority to leave the study any time throughout the study.

18.2 Indicate how the research team is permitted to access any sources of information about the subjects.

NOTE: Examples of appropriate responses include: school permission for review of records, consent of the subject, HIPAA waiver. This question **does apply** to records reviews.

Response:

Consent forms are provided to all orthodontics patients for completion prior to the initial bonding appointment once they are accepted as patients in our orthodontic clinic. These consent forms include privacy consents and HIPAA waivers. The patients will be informed that their private information will be used only for educational and research purposes within the University at Buffalo School of Dental Medicine's Orthodontic Clinic.

19.0 Data Management and Analysis*

19.1 Describe the data analysis plan, including any statistical procedures. This section applies to both quantitative and qualitative analysis.

Response:

Intra-examiner reliability will be addressed by randomly selecting 5 lateral cephalograms 2 weeks after initial measurements were performed and having the same operator (AN) repeat the landmarking, superimpositions and measurements. The same operator will also repeat measurements on 5 casts 2 weeks after measurements are conducted for the maxillary first molar and canine rotational measurements. Intra-class correlation coefficients will be calculated in order to determine intra-examiner reliability based on the first and second measurements (P < 0.05).

Statistical analysis will be performed using SPSS. A Shapiro-Wilk test will be run to assess for normality. If the data are normally distributed, independent ttests will be ran to compare means between the two treatment groups. If normality assumptions are not met, a Wilcoxon Rank-Sum test will be used to compare means between the two treatment groups for all measurements.

19.2 If applicable, provide a power analysis.

NOTE: This may not apply to certain types of studies, including chart/records reviews, survey studies, or observational studies. This question is asked to elicit whether the investigator has an adequate sample size to achieve the study objectives and justify a conclusion.

Response:

Sample size estimation: Based on a power of 80% and a significance level of 0.05, it was determined that a sample of size of 16 per treatment group, or a total of 32 participants, would be sufficient in order to have a standardized effect size of 1.02366. These calculations were made based on mean values reported for total treatment time (in months) to achieve Class II correction using a CMA in previous studies. ^{12,14,15,16}

19.3 Describe any procedures that will be used for quality control of collected data.

Response:

One investigator (AN) will be mapping lateral cephalometric radiographs and performing all measurements on patient records, as well as fabricating all inoffice appliances and mandibular essix retainers to reduce heterogeneity. The research examiner and supervisors will be ensuring that the data is good quality and is adequate for analysis. All patient records and data will be encrypted, deidentified and properly stored and secured on our computer network. A Code Key file will be stored in a separate protected drive.

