2.0 Objectives*

2.1 Describe the purpose, specific aims, or objectives of this research.

Response:

The aim in this study is to explore the efficacy and efficiency of Class II molar correction with the sagittal first approach using either a sectional, in-office fabricated appliance or the CMA by measuring total treatment duration (in months) as well as comparing dental and skeletal measurements taken from lateral cephalometric radiographs obtained prior to Class II correction (T0) and immediately after removal of the appliance (T1). We will also be comparing secondary molar and canine rotational movements after Class II correction by comparing digital dental casts obtained at T0 and T1.

2.2 State the hypotheses to be tested, if applicable.

NOTE: A hypothesis is a specific, testable prediction about what you expect to happen in your study that corresponds with your above listed objectives.

Response:

1. There is no difference in mean duration (in months) of Class II molar correction when using a CMA or an in-office Class II correction appliance.

- 2. There is no difference in mean skeletal changes (in millimeters, degrees) after Class II correction using CMA or an in-office Class II correction appliance.
- 3. There is no difference in mean dental changes (in millimeters, degrees) after Class II correction using CMA or an in-office Class II correction appliance.

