5.0 Study Design*

5.1 Describe and explain the study design (e.g. case-control, cross-sectional, ethnographic, experimental, interventional, longitudinal, observational).

Response:

This will be a pilot randomized clinical controlled trial including males and females with a unilateral or bilateral ½ cusp to full cusp Class II molar and canine relationship and mild to moderate crowding. The sample consists of adolescent patients who are receiving comprehensive full fixed appliance orthodontic treatment at the Postgraduate orthodontic clinic at the UBSDM. Subjects will be randomized into one of two treatment groups. Subjects will receive Class II correction prior to orthodontic treatment using either the CMA or an in-office fabricated Class II correction appliance. Lateral cephalometric radiographs and digital models will be taken at: T0 (initial records appointment) and T1(the appointment where the appliance is removed once Class II molar correction has been achieved). Patients in both treatment groups will use the same mandibular anchorage protocol (essix with 2 mm thickness and a button bonded to the buccal surface of the mandibular first molars). Elastic progression for both treatment groups will follow the protocol recommended by the CMA manufacturer (Force 1 Class II elastics (1/4, 6 oz) will be worn for 1 month, and Force 2 Class II elastics (3/16, 8 oz) will be worn for the remainder of Class II correction). Dental and skeletal changes will be measured using lateral cephalometric radiographs taken at T0 and T1, and rotational movements of the maxillary first molar and canine will be assessed using superimposition of the maxillary models taken at T0 and T1 using the e- model Compare 8.1 software by Geodigm. Treatment duration will be calculated (in months) starting on the date the appliance was bonded and ending on the date of appliance removal. Treatment duration and dental and skeletal movements will be compared between the two treatment groups.

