Isolation will then be removed and the patient will be instructed to wear the essix retainer 24 hours a day and to only take it out to eat and when completing hygiene methods. The patient will be given Force 1 Class II elastics (1/4, 6 oz) and will be instructed on how to place them from either the hook on the canine pad (CMA group) or the hook on the canine bracket (in-office appliance group) to the button on the mandibular first molars. The patient will be instructed to wear the elastics 24 hours a day and to only remove them when eating and completing hygiene methods, and to change elastics daily.

The patient will be seen 1 month later and will be given Force 2 Class II elastics (3/16, 8 oz) and will be instructed to wear them using the same protocol for the remainder of their class II correction. The patient will be evaluated each month until a Class I molar and canine relationship has been obtained.

Once a Class I molar and canine relationship has been obtained, The CMA or in office appliance will be removed, and an intraoral scan and lateral cephalometric radiograph will be taken immediately after removal of the appliance(s) (T1). The

total duration (in months) of Class II correction, starting at the bonding appointment and ending at the T1 appointment will be recorded for each subject.

Superimposition & Data Analysis

Once T0 and T1 records are obtained, lateral cephalometric tracing and measurements will be completed and recorded by one operator (AN). Superimpositions will be constructed using T0 and T1 lateral cephalometric tracings. Initial cephalometric measurement (T0) will be subtracted from final cephalometric measurements (T1) for each value (Please see table in section 12.2 for a complete list of lateral cephalometric measurements and their descriptions).

Intraoral scan data will be collected with an iTero Element 3D Scanner. Digital models will be superimposed using the Best fit method described in a study conducted by Grünheid and Larson. Maxillary model superimpositions will be used to address the difference in maxillary first molar and canine rotational positions before versus after Class II correction (°). Mean values for all measurements (lateral cephalometric and digital model superimposition) will be calculated for each treatment group and statistical analyses will be ran using he Statistical Package for the Social Sciences (SPSS) to compare means.

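### Section 19.1 lets a normality pre-test replace the t-test with a rank-sum test, which it wrongly says compares means, so the mean difference in hypotheses 1-3 may go untested

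*Protocol*

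**What the plan says.** - **Hypotheses (Protocol 2.2).** All three are null hypotheses about means. The first reads "There is no difference in mean duration (in months) of Class II molar correction"; the second and third concern mean skeletal and mean dental changes.
- **Analysis (Protocol 19.1).** A Shapiro-Wilk test comes first. "If the data are normally distributed, independent ttests will be ran to compare means between the two treatment groups". If normality fails, "a Wilcoxon Rank-Sum test will be used to compare means between the two treatment groups for all measurements".
- **Sample size (Protocol 19.2).** 16 per arm, 80% power, significance level 0.05, standardized effect 1.02366, based on mean CMA treatment times from earlier studies. No SD is given.
- **Outcome construction (Protocol 5.1 and 12.1).** Duration is counted "starting on the date the appliance was bonded and ending on the date of appliance removal", and "The patient will be evaluated each month until a Class I molar and canine relationship has been obtained". For the cephalometric outcomes, "Initial cephalometric measurement (T0) will be subtracted from final cephalometric measurements (T1) for each value". Descriptively, "Mean values for all measurements (lateral cephalometric and digital model superimposition) will be calculated for each treatment group".

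**The concern.** The rank-sum test asks whether values in one arm tend to exceed those in the other. That coincides with a test of means only if the two distributions have the same shape and differ by a shift. Section 19.1 gives both branches the same purpose, so it misdescribes the second.

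The observed data then decide which quantity is tested. If the pre-test passes, the trial tests the mean difference it was sized for. If it fails, the planned test concerns something else, yet the report would follow 19.1 and call the result a comparison of means. This is stated in the protocol itself, so it is not a detail left for a statistical analysis plan.

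**Working it through.** **1. The plan's own figure.** Two-sample t-test, two-sided 0.05, n = 16 per arm, df = 30. Noncentrality = 1.02366 × √(16/2) = 2.895, which gives power 0.79999. Solving for n gives 16.0001. The stated N is therefore correct, and the stated effect is the smallest one a two-sided t-test detects with 80% power at 16 per arm. The 95% CI half-width is t(0.975, 30) × √(2/16) = 2.042 × 0.3536 = 0.722 SD.

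The rank-sum branch was not sized. Under normality its relative efficiency is 3/π = 0.955, so 16 per arm acts like 15.28 and power is about 78% (77.3% by simulation).

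**2. Error rate of the two-stage rule.** Assumed: Shapiro-Wilk in each arm at 0.05, with a switch if either arm fails. With identical distributions in the two arms (normal, or log-normal with log-SD 0.4, 0.6, 0.8), rejection was 4.8% to 5.5% over 20,000 runs.

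With equal means of 4.6 months, log-normal data and unequal spread (ranges cover repeat simulations):

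| SD ratio | Two-stage rule | t-test |
|---|---|---|
| 1.5 | 5.9-6.2% | 4.9-5.3% |
| 2 | 7.5-9.3% | 5.2-6.3% |

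If skew is made stronger at SD ratio 2 (log-SD 0.4, 0.6, 0.8 in both arms), the two-stage rule rejects in 8.4%, 12.2% and 17.8%, against 5.8%, 6.3% and 6.7% for the t-test. Both unequal spread and skew are needed for a material excess.

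**3. How often duration would be switched.** Exactly normal data already fail in 1 − 0.95² = 9.75% of trials. Monthly review can add to this, because removal dates cluster near monthly steps. Assumed: normal true correction times, mean 4.1 months, SD 1 month, removal at the first visit on or after correction, per-arm test at 0.05.

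| Visit-date jitter (SD) | Visits tied to fixed monthly dates from bonding | Each visit booked from the last |
|---|---|---|
| 0 days | 85-88% | same by construction |
| 3 days | 39-40% | 15-16% |
| 7 days | 13-14% | 9-10% |

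The protocol gives neither the SD of duration nor the regularity of visits. A larger SD lowers the fixed-date figures (42%, 19% and 10% at SD 1.5).

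**4. Cephalometric outcomes: T0 as covariate against change score.** Assume equal variances at T0 and T1 and correlation ρ. The change score has variance 2(1 − ρ)σ² and ANCOVA has residual variance (1 − ρ²)σ², so the ratio is (1 + ρ)/2. Multiply by 1.036 for estimating one slope with 32 patients:

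- ρ = 0.5: 0.75 × 1.036 = 0.78
- ρ = 0.8: 0.90 × 1.036 = 0.93
- ρ = 0.9: 0.95 × 1.036 = 0.98
- break-even: ρ = 2/1.036 − 1 = 0.93

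**5. Power given up by dropping the switch.** Pure shift of 1.02366 SD, t-test against two-stage rule: 80% v 80% (normal), 81% v 83% (log-normal sigma 0.3), 82% v 89% (sigma 0.5).

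**The case against.** The strongest reply is that little changes in practice. If the appliances differ by a shift, both tests address the same null hypothesis. With exactly monthly visits and SD 1 month, t-test and rank-sum reach the same verdict in 98% of simulated trials under the null and 95% under the planned shift. Under skew the two-stage rule has more power. Section 12.1 also has group means calculated for the cephalometric and model measures whichever branch is used, and this is a pilot.

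Most of that stands, and it limits the point to interpretation. It does not remove it. A table of means is not a test or an interval for their difference, and the shift assumption is not stated anywhere.

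A reader might infer more than the documents support:

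- **That the primary outcome is likely to be switched.** The high figures need visits almost exactly on schedule. With visits booked one from the next, switching falls close to the 10% expected for normal data.
- **That one failed measure moves every measure to the rank-sum test, almost certainly.** This needs a strained reading of the phrase on all measurements, and independence between measures. Section 12.2 rules out independence: for example, the maxillomandibular differential is computed from two other listed lengths.
- **That the missing pre-test level, or the choice between per-arm and pooled testing, is a fault.** That is ordinary content for a statistical analysis plan.
- **That change scores, or an unadjusted comparison of duration, are invalid.** Both are valid under randomization; a covariate only affects precision. Adjusting duration for T0 molar relationship would also need a rule for which side counts in unilateral cases, and the protocol has none.

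**Conclusion.** The point holds as a misdescribed test and a data-driven choice of the quantity tested. Section 19.1 should be corrected, because it governs the primary analysis and conflicts with sections 2.2 and 19.2. The sample size is right for the t-test branch.

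It is not a finding of a seriously inflated error rate. The two-stage rule stays near 5% unless the arms differ in spread and the data are skewed: about 6% v 5% at SD ratio 1.5, and 8-9% v 6% at ratio 2, under the assumed log-normal data with mean 4.6, and more only with stronger skew. The frequency of switching, about 9% to 88% at an assumed SD of 1 month, is a range that the documents do not narrow. All these figures assume a per-arm pre-test at 0.05. The gain from T0 covariates depends on a correlation the protocol does not give.

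**What to change.** In section 19.1, remove the Shapiro-Wilk switch and state:

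- **Duration:** one pre-specified test of the mean difference (for example Welch t) with a 95% CI.
- **Cephalometric outcomes:** ANCOVA of the T1 value on treatment and its own T0 value, reporting the adjusted mean difference with a 95% CI.
- **Rotations:** mean difference in change with a 95% CI, since superimposition yields the change directly.
- **Rank-sum test:** a sensitivity analysis, described as a rank comparison and not as a comparison of means.

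This is a change of wording and needs no new data. N stays at 16 per arm; simulated power at the planned effect is 80.2% (Student) or 80.1% (Welch). The costs are some power against the two-stage rule if durations are strongly skewed (82% v 89% at log-normal sigma 0.5, Student t-test) and one degree of freedom per ANCOVA, which brings no gain where the T0-T1 correlation exceeds about 0.93.

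### Hypotheses 2 and 3 are each one null but are tested through 14 or 15 separate comparisons with no key measure, so each hypothesis's false-rejection chance can exceed 5%

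*Protocol*

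**What the plan says.** Protocol section 2.2 lists three hypotheses. The first concerns treatment duration. The second reads "There is no difference in mean skeletal changes (in millimeters, degrees) after Class II correction using CMA or an in-office Class II correction appliance", and the third "There is no difference in mean dental changes (in millimeters, degrees) after Class II correction using CMA or an in-office Class II correction appliance". Each of these two is written as a single null covering a whole class of measurements.

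Section 12.2 tabulates the cephalometric measurements, and section 12.1 adds molar and canine rotation from the superimposed digital models. Section 19.1 prescribes a Shapiro-Wilk check, then an independent t-test or a Wilcoxon rank-sum test, "to compare means between the two treatment groups for all measurements". It names no leading measure, global test or rule for deciding when hypothesis 2 or 3 is rejected.

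The only significance level attached to a group comparison is in section 19.2: "Based on a power of 80% and a significance level of 0.05". That paragraph sizes the trial on treatment duration. The study summary calls the trial a pilot and places the skeletal and dental comparisons under secondary objectives.

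**The concern.** A null of no difference across a set of measurements is false as soon as one of them differs. Without another rule, the natural reading is that one significant measurement rejects the hypothesis. With 14 or 15 chances per hypothesis, the error rate of the hypothesis is no longer the error rate of a single test. At stake is a report that one appliance differs from the other in skeletal or dental effect, presented as the rejection of a prespecified hypothesis, when the result is chance.

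**Working it through.** **1. The plan's own figure.** Section 19.2 states "a sample of size of 16 per treatment group, or a total of 32 participants" and an effect size of 1.02366 SD at 80% power. A two-sample t-test with two-sided alpha 0.05 and 16 per group has power 0.800 at d = 1.02366 (noncentral t), and solving for n gives 16.0 per group. A one-sided test at 0.05 would have power 0.88, so it does not match. The stated level is therefore a two-sided 0.05, and it was set for duration.

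**2. Counting the tests (sections 12.1 and 12.2).**
- Skeletal: 3 maxillary + 3 mandibular + 3 maxillomandibular + 6 vertical = 15. Two vertical rows carry the same label, but their descriptions use different reference planes, so they count as two.
- Dental: 12 dentoalveolar measurements (the X and Y axes are reference lines, not outcomes) + 2 model rotations = 14. IMPA and L1-MP describe the same angle. Counted once, they leave 13.

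**3. Assumptions.** Each test is two-sided at 0.05. Any one p < 0.05 rejects the hypothesis. There are 16 subjects per group and no true difference in any measurement. The correlation between measurements is not in the protocol, so it is varied.

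**4. Upper bound, independent tests.** P(at least one p < 0.05) = 1 - 0.95^k:
- k = 13: 1 - 0.95^13 = 0.487
- k = 14: 1 - 0.95^14 = 0.512
- k = 15: 1 - 0.95^15 = 0.537

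**5. Correlated tests.** Simulated t-tests with 16 per group, a common correlation between all measurements in a family, and 200,000 runs per cell (simulation error about 0.1 percentage point):

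| Assumed correlation | 13 tests | 14 tests | 15 tests |
|---|---|---|---|
| 0.5 | 34.2% | 35.3% | 36.9% |
| 0.7 | 24.8% | 25.6% | 26.4% |
| 0.9 | 14.1% | 14.4% | 14.8% |

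**6. A less uniform structure.** Here measurements of the same type correlate at 0.7 to 0.9 and measurements of different types at 0.2 to 0.5 (20,000 runs). The chance is 26-37% for the dental family and 27-39% for the skeletal family.

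**7. Overlap in the list.** ANB follows from SNA and SNB, the maxillomandibular differential is Co-Gn minus Co-A, and IMPA repeats L1-MP. Independence is therefore implausible, and the true figure probably lies below the 51-54% bound.

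**8. For comparison.** A Bonferroni level that held each hypothesis at 5% would be 0.05/14 = 0.0036 (dental) or 0.05/15 = 0.0033 (skeletal).

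**The case against.** The strongest reply is that this is an omission. Ranking secondary measures and setting multiplicity rules are commonly left to a statistical analysis plan, one may exist, and the protocol never claims 5% control for hypotheses 2 and 3. That would answer a complaint about a missing adjustment. It does not fully answer this one, because the protocol itself fixes both parts: one null per class in 2.2, and a test of every measurement in 19.1. Those parts do not fit together without a rule.

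Two further objections stand as limits:
- The 0.05 level comes from the sample size paragraph, which concerns duration. The other P < 0.05, in 19.1, belongs to the reliability coefficients. Applying 0.05 to these tests is an inference.
- The hypotheses are worded in the plural with mixed units, so they can be read as shorthand for one null per measurement, each with its own 5% error. On that reading there is no inflation of a stated hypothesis, but nothing in the text says this is meant.

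The pilot label, the secondary ranking and the exploratory aim lower the stakes. They do not remove the point, because 2.2 lists these nulls beside the primary one and nothing labels their tests descriptive.

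**Conclusion.** The point holds, at modest weight. If each test uses 0.05 and any one significant result rejects, the false-rejection chance for hypothesis 2 or 3 is about 14-15% at a common correlation of 0.9, about 26% at 0.7, 35-37% at 0.5, and at most 51-54%. Every assumption tried puts it well above 5%.

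Three stronger readings are tempting and are not supported:
- **About 26% is a floor.** It is not. It rests on an assumed correlation near 0.7, and higher correlation gives less.
- **The trial is likely to report a false difference.** Over all 29 tests the chance is 77% under independence (1 - 0.95^29 = 0.774), but 51% at correlation 0.5 and 35% at 0.7. Likely is too strong unless the measurements are close to independent.
- **The trial's main conclusion is at risk.** It is not. Treatment duration is one hypothesis with one test.

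**What to change.** In sections 2.2 and 19.1, before any data are seen, name one key skeletal and one key dental measure. State that each is tested at 0.05 and is the sole test of hypothesis 2 or 3 respectively. Report all other measurements as mean differences with 95% confidence intervals, labelled exploratory, with no accept or reject statement. Alternatively, restate hypotheses 2 and 3 wholly as exploratory estimation, with no test.

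No Holm step across the two key tests is needed for this purpose, since one test per hypothesis already holds each at 5%. The detectable difference at 80% power for a key measure stays at 1.02 SD. Testing all 15 skeletal measures with a Bonferroni adjustment would instead raise it to about 1.44 SD (alpha 0.05/15, 16 per group).

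The cost is protocol wording only, with no new data, visits or subjects. The downside is that no formal significance claim can be made on the non-key measures.
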